ORI IRB# 00000278

IRB Approved on April 14, 2021

Protocol Version: July 26, 2024

Official Title: Integrated Smart Speaker/Mobile Application to Promote Positive Parenting Among Caregivers of Youth with Challenging Behaviors

Principal Investigators: [name]., [name]., [name].

Oregon Research Behavior Interventions Strategies Inc., dba Influents Innovations

Award No. R43MH124577-01A1

Final Version Dated: July 26, 2024

STUDY PROTOCOL

FamilyNet Intervention Overview. The FamilyNet (FN) prototype app is an integrated and coordinated smart-speaker/mobile application designed to support families' successful implementation of behavior plans, an empirically supported behavioral parenting strategy to promote positive behavior change in children. Over the course of four weeks, the experience progresses through (1) a monitoring phase, in which caregivers identify a positive behavior they would like for their child to increase, and learn to observe their child's behavior to establish reasonable and reachable goals; (2) construction of a behavior plan, in which, working with research staff, parents and youth align on goals and rewards and build a positively framed, individualized behavior plan within the web/mobile app; and (3) families use of the web-app and integrated smart speaker app to implement their behavior plan, receive reminders, and report and track their progress on the plan. The family's behavior plan is reinforced with a system of rewards that the FamilyNet technology supports with reminders and prompts. FamilyNet features caregiver-facing and youth-facing components: Caregivers interact with the web/mobile app for reporting and tracking their progress and receiving reminders, and youth use the smart speaker for these functions.

Participant Recruitment and Enrollment Procedures. A feasibility trial was conducted to evaluate the FamilyNet program's feasibility, utilization, and user satisfaction in families of at-risk youth. Families of youth ages 10 to 17 exhibiting challenging behaviors were recruited to participate in the feasibility study via distribution of study information through family counseling centers, family service agencies, youth-serving agencies, and targeted advertising on Facebook and LinkedIn. Therapists and practitioners at the family- and youth-serving agencies were encouraged to describe the study and distribute the study materials to their client families who they thought might benefit from the extra support with behavior plans that FamilyNet would provide. LinkedIn advertising also targeted family- and youth-serving therapists who might find

FN helpful for the families they served. Facebook advertising targeted families of youth directly. Interested caregivers who contacted project staff were provided additional information about the study and screened for eligibility; those eligible were sent the informed consent form.

Eligibility Criteria. Eligible families were primary parent/caregivers who had children ages 10 to 17 years old who lived with them at least half the time; had a smartphone (either Android or iOS) and access to email; and spoke English. Families were excluded if the target-age child had a developmental disability severe enough that the child was unable to speak and/or follow simple directions.

Intervention and Assessment Procedures. After caregivers signed the consent and the youths signed the youth assent, primary caregivers completed the pretest (T1) questionnaire (online, on the Qualtrics platform) and then were scheduled for a phone call with research staff. In this phone call, caregivers were guided in downloading the FamilyNet web-app onto their phones and in setting up their smart speakers, and then guided in choosing the positive behavior that they wanted to increase in their target child. They were asked to monitor that behavior on the web-app for three days. After the monitoring phase, a Zoom session was scheduled with caregiver and youth, in which research staff guided the caregiver and youth through a series of psychoeducational slides, and then guided the caregiver and youth in setting goals for behavior change and developing a behavior plan with rewards. Caregivers and youth were asked to engage with the FN program for 4 weeks. Research staff provided prompts during the 4-week period to encourage usage and provide technical support as needed. At 4 weeks after T1, caregivers were administered the posttest (T2) caregiver questionnaire, and youth were administered the T2 youth questionnaire; both T2 questionnaires were administered online on the Qualtrics platform. This design allowed evaluation of T1-T2 change and satisfaction/usability of the FamilyNet prototype. Caregivers received \$25 for completing the T1 assessment, and \$50 for completing the T2 assessment. Youth received \$20 for completing their T2 questionnaire.

Measures. T1 and T2 questionnaires measured (1) primary caregivers' parenting practices (Program-Targeted Parenting Practices (PTPP): Frequency of Engagement and Satisfaction with Handling Child's Behavior subscales; Parenting Practices Inventory (PPI): Inconsistent Discipline and Positive Reinforcement subscales); (2) caregivers' self-efficacy (PTPP), (3) family relationships (CASY scale, adapted from Family Environment Scale and Conflict Behavior Questionnaire: Positive Family Relations; Parent-Child Conflict), and (4) youths' behavior (Strengths and Difficulties Questionnaire (SDQ): Emotional Problems, Conduct Problems, Hyperactivity, Peer Problems, Prosocial, and Total Difficulties scores; Parent Daily Report (PDR): Positive Child Behaviors and Negative Child Behaviors; PTPP: Frequency of Child's Positive Behavior and Parent Satisfaction with Child's Behavior). The T2 caregiver and youth questionnaires also contained measures of caregivers' and youths' ratings of (5) satisfaction and acceptability, and (6) usability of the FamilyNet program. Demographics were collected from caregivers at T1. Usage data for the web-app and the Alexa skill were collected to measure families' usage of FN.

Analytic Plan. The evaluation had three main goals: (1) establish the initial efficacy of the FamilyNet program in improving caregivers' parenting practices and self-efficacy, family relationships, and the youths' behavior outcomes; (2) determine the participants' perception of usability, acceptability, and satisfaction regarding the FamilyNet program; and (3) and examine program usage. Paired t-tests were used to examine pretest-to-posttest change to determine whether there were meaningful improvements in caregiver and youth outcomes after engaging with the FN program. Cohen's d provided the measure of effect size, with the convention of .20 = small, .50 = medium, and .80 = large. With 15 families with both T1 and T2 data, the study was powered to detect significant change in outcomes associated with large effects ($d > .78$). Thus, in addition to statistical significance, we interpreted effect sizes of Cohen's d of .25 or greater as initial evidence that parenting and child outcomes showed meaningful change after engaging with the FamilyNet program. Examination of descriptive statistics for the user satisfaction and acceptability items at T2 informed on participants' reactions to the program. A descriptive summary of the program usage data provided evaluation of families' use of the FamilyNet program.

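### Goal 1 claims to establish initial efficacy, which a single-arm pre-post study rated by the participating caregiver cannot do

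*Combined protocol and SAP*

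**What the plan says.** The combined protocol and SAP describes the study's purpose in more than one way.

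- Participant Recruitment and Enrollment Procedures: "A feasibility trial was conducted to evaluate the FamilyNet program's feasibility, utilization, and user satisfaction in families of at-risk youth".
- Intervention and Assessment Procedures: "This design allowed evaluation of T1-T2 change and satisfaction/usability of the FamilyNet prototype".
- Analytic Plan, first of three main goals: "establish the initial efficacy of the FamilyNet program in improving caregivers' parenting practices and self-efficacy, family relationships, and the youths' behavior outcomes". The other two goals cover usability, acceptability and satisfaction, and program usage.

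The analysis for goal 1 is a within-family comparison: "Paired t-tests were used to examine pretest-to-posttest change". The Analytic Plan gives the sample ("With 15 families with both T1 and T2 data") and a detectable effect of d > .78. It then adds a second, lower criterion: "in addition to statistical significance, we interpreted effect sizes of Cohen's d of .25 or greater as initial evidence" of meaningful change following use of the program.

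On who was enrolled, the recruitment section says that the youth were showing challenging behaviors. The routes included "distribution of study information through family counseling centers, family service agencies, youth-serving agencies" and social-media advertising, and therapists were encouraged to pass the materials to client families they thought could gain from it. Eligibility Criteria sets no severity threshold.

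On who rated, only the primary caregiver completed T1. Youth completed a questionnaire at T2 only. The intervention overview has caregivers using the app themselves.

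**The concern.** To establish efficacy in improving an outcome is a causal claim. It needs some basis for saying what would have happened to the same families over the same four weeks without the program, and the documents describe none.

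Several other processes would move scores in the favorable direction:

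- **Regression to the mean.** Families recruited while behavior is a problem may be nearer their usual level four weeks later.
- **Time trends.** Behavior and family routines can change over four weeks for unrelated reasons.
- **Concurrent services.** Recruitment ran partly through therapists' existing clients, and Measures lists nothing on other help received.
- **Rater expectancy.** The caregiver chose the target behavior, used the program and then rated the result.

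A paired t-test on one group cannot separate these from a program effect. If goal 1 stands, a favorable T1-T2 change would be reported as efficacy that the study did not test. The label of youth outcomes would also suggest a source independent of the caregiver, and there is none.

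**Working it through.** **1. The plan's own figure.** For a paired t-test with n = 15 (14 df), two-sided alpha .05 and 80% power (both assumed, since neither is stated), the noncentral t gives a detectable d of 0.778. Power at d = .78 is 80.2%. The stated d > .78 reproduces and is not in dispute.

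**2. Where the .25 bar sits.** The smallest observed paired d with two-sided p < .05 is t(.975, 14)/√15 = 0.554. Power at a true d of .25 is 15%. With no true change of any kind, a single outcome still reaches an observed paired d of .25 in 17.5% of studies of this size.

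**3. Who rates the outcomes.** Measures lists 17 T1-T2 scores by my count: 4 parenting, 1 self-efficacy, 2 family relations, and 10 under youth behavior (6 SDQ, 2 PDR, 2 PTPP). Without a youth questionnaire at T1, no youth-rated change can be formed. All 17 change scores are therefore caregiver-rated.

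**4. Regression to the mean, as an illustration.** Inputs, both assumed because the documents give neither:

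- r: four-week retest correlation, .6 to .9.
- z: distance of the enrolled families' T1 mean from the mean toward which their scores regress, in population SDs, 0.5 to 1.5.

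With zero program effect and equal variances at T1 and T2:

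- Expected change in population SDs = (1 − r)z.
- SD of the differences = √(2(1 − r)), so expected paired d = (1 − r)z / √(2(1 − r)) = z√((1 − r)/2).

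The plan does not say which SD standardizes Cohen's d, so each cell shows population-SD units, then paired-difference units:

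| | z = 0.5 | z = 1 | z = 1.5 |
|---|---|---|---|
| r = .6 | .20 / .22 | .40 / .45 | .60 / .67 |
| r = .7 | .15 / .19 | .30 / .39 | .45 / .58 |
| r = .8 | .10 / .16 | .20 / .32 | .30 / .47 |
| r = .9 | .05 / .11 | .10 / .22 | .15 / .34 |

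In population-SD units the expected value exceeds .25 in 5 of 12 cells and falls short in 7. In paired-difference units it is 7 above and 5 below.

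**5. Chance of passing with n = 15 and zero program effect.** Observed paired d times √15 follows a noncentral t with 14 df and noncentrality equal to expected paired d times √15.

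| Assumed values | Observed d ≥ .25 | Significant favorable t-test |
|---|---|---|
| r = .9, z = 0.5 | 30.5% | 6.0% |
| r = .7, z = 1 | 70.5% | 28.7% |
| r = .6, z = 1.5 | 94.7% | 67.6% |

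The criterion is worded so that d ≥ .25 could stand alone or be required together with significance. If both are required, the last column applies, because significance already needs d of at least .554.

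**The case against.** The best defense is that the overclaim lies in one sentence. The study calls itself a feasibility trial, goal 1 speaks only of initial efficacy, and the interpretive sentence describes change that follows program use, which is a temporal statement. That is fair, and it limits how much text must change. It does not rescue the goal: calling efficacy initial lowers the claimed strength of evidence but leaves the claim causal.

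Several stronger readings are tempting, and the documents do not support them.

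- **That regression to the mean does pass the bar.** This depends on assumed r and z. At the midpoints, r = .75 and z = 1, (1 − r)z is exactly .25, and 7 of 12 cells in population-SD units are below it. The formula also supposes that enrollment is tied to the T1 score. There is no severity cut-off, and families enrolled for long-standing difficulty would regress less. The argument is clearest for child behavior and parent-child conflict, and less direct for parenting practices and self-efficacy.
- **That most or many families were in counseling.** No proportions are given, and advertising was another route.
- **That building the plan with staff is a confounder.** The intervention overview makes staff-supported plan construction a phase of FamilyNet, so it is part of what is being evaluated.
- **That efficacy is the primary goal and feasibility was displaced.** Being listed first is not a designation as primary. Satisfaction, usability and usage are already main goals.

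It can also be said that rewording a goal once the analyzed sample is known is post hoc. That is true, but this change narrows the claim and cannot favor the program.

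**Conclusion.** The concern holds for the goal statement and for what may be concluded from d ≥ .25 or p < .05. Goal 1 is wrong as written because the design has no means of attributing T1-T2 change to FamilyNet. This rests on the documents alone: no comparison group, recruitment on current problems, and caregiver-only ratings of change. It would hold even if regression to the mean were nil.

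The numerical part is illustrative. Under the assumed ranges, regression to the mean alone contributes .05 to .60 population SD, which straddles the plan's bar of .25. The effects of time trends, concurrent services and expectancy cannot be sized from the documents. The power statement is correct and needs no change.

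**What to change.** - Restate goal 1 as: estimate caregiver-reported T1-T2 change, with 95% confidence intervals, to inform a controlled trial.
- State that neither d ≥ .25 nor p < .05 is treated as evidence of efficacy. The interval makes the precision plain. With n = 15 its half-width is 0.554 SDs of the differences, so an observed paired d of .25 corresponds to −.30 to .80 (.25 ± .554).
- Label the youth outcomes as caregiver-reported youth behavior.
- List regression to the mean, time trends, concurrent services and rater expectancy as alternative explanations that the design cannot exclude.
- Date the change and say that it was made after the number of analyzed families was known.

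A question on concurrent services at T1 and T2 is not a usable remedy here. The document is in the past tense and already reports 15 families with both assessments, so such a question belongs in a later study.

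The cost is a few sentences of rewording, with no new data and no change to the tests. The real price is that the study can no longer claim initial efficacy.

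### T1-T2 change is judged by a paired t-test and a bare Cohen's d from 15 pairs, with no confidence interval and no stated denominator, although each d carries a 95% interval about one d unit wide

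*Combined protocol and SAP*

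**What the plan says.** The Analytic Plan of the combined protocol and SAP is one paragraph. For change between T1 and T2 it names two outputs. The first is the test: "Paired t-tests were used to examine pretest-to-posttest change". The second is the effect size: "Cohen's d provided the measure of effect size, with the convention of .20 = small, .50 = medium, and .80 = large".

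The sample is given as "With 15 families with both T1 and T2 data", and the plan states that "the study was powered to detect significant change in outcomes" for large effects only, with d above .78. Because of that limit it adds a second criterion alongside significance: "we interpreted effect sizes of Cohen's d of .25 or greater as initial evidence" of meaningful change.

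The Measures section lists 17 caregiver-reported scores taken at both T1 and T2. Neither section, nor any other part of the document, mentions a confidence interval, a standard error of d, a small-sample correction, or the denominator of d for paired data.

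**The concern.** The plan accepts that significance testing is informative here only for large effects, and so leans on the size of d. The precision of d then decides how much each result can bear, and no measure of precision is planned. A label of small, medium or large, or a d on one side of .25, looks like a finding even when the data cannot separate no change from a medium change. This applies in both directions: to outcomes counted as initial evidence and to outcomes that miss the cut-off.

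The missing denominator adds to this. A reader who knows n can rebuild an interval from d only if d was divided by the SD of change. If the baseline SD or the average of the T1 and T2 SDs was used, the T1-T2 correlation is needed as well, and the plan does not give it.

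**Working it through.** **Inputs.** From the Analytic Plan: n = 15 pairs (14 df), paired t-test, medium = .50, cut-off .25, detectable d = .78. Not stated, so assumed: two-sided alpha .05, 80% power, and d standardised by the SD of change. Positive d means improvement.

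**Step 1: reproduce .78.** For a paired t-test, t = d × √n follows a noncentral t distribution with 14 df and noncentrality (true d) × √15. At two-sided .05 and 80% power the smallest detectable d is .778, and power at d = .78 is 80.2%. The plan's figure reproduces on the SD-of-change scale. One-sided .05 at 80% power gives .675 and two-sided .05 at 90% gives .901, so neither matches.

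**Step 2: the smallest significant d.** The critical t at 14 df is 2.145, so the critical d is 2.145 / √15 = 2.145 / 3.873 = .554.

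**Step 3: 95% intervals for d.** These invert the noncentral t: find the noncentrality values at which the observed t sits at the 97.5th and 2.5th percentiles, then divide by √15.

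| Observed d | 95% interval | Width |
|---|---|---|
| .00 | -.51 to .51 | 1.02 |
| .15 | -.36 to .66 | 1.02 |
| .25 | -.27 to .76 | 1.03 |
| .50 | -.05 to 1.03 | 1.08 |
| .80 | .20 to 1.37 | 1.17 |

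The whole small-to-large scale spans .80 - .20 = .60, which is less than any of these widths. Every observed d from .25 to about .55 has an interval that includes 0. Every observed d from about -.01 to .25 has an interval that includes .50.

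**Step 4: how often a medium effect misses the cut-off.** If the true d is .50, the noncentrality is .50 × 3.873 = 1.936. The probability that the observed d falls below .25 is .166, about 17%. Power is .438, so the probability of a non-significant result is 1 - .438 = .562. Of that, .562 - .166 = .396 lies between .25 and .554, where the plan still counts the result as initial evidence.

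**Step 5: small-sample bias.** The Hedges factor at 14 df is J = Γ(7) / (√7 × Γ(6.5)) = .945. Uncorrected d is too large on average by 1/.945 - 1 = 5.8%. At .25 this is .25 × .058 = .0145, about .015, against an interval half-width of about .51. If d is divided by the average of the T1 and T2 SDs, simulation over T1-T2 correlations from 0 to .9 gives a bias of about 3% to 5%. With the baseline SD it is again about 6%.

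**The case against.** The strongest reply is that the imprecision comes from having 15 families, that the plan discloses its limited power, and that an interval shows the problem without curing it. The study is presented as a feasibility trial, efficacy is one of three goals and is called initial, and the paragraph describes analyses without laying out tables. All of this stands, and it limits the weight of the point. It does not remove it. The plan names its test, effect size, labels and cut-off, and a reading based on d needs the precision of d beside it. That no interval or correction is planned is inferred from the document's silence.

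A reader might infer more than the document supports:

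- *That low, non-significant outcomes will be declared unchanged.* The plan never says so. Because of its .25 criterion, non-significance alone is not a negative verdict.
- *That a medium effect is missed 56% of the time.* That is the chance of non-significance. About 40 of those 56 percentage points lie between .25 and .55 and count as initial evidence; about 17% fall below .25.
- *That useful parts of the program will be discarded.* The document evaluates FamilyNet as a package and ties no decision about its parts to these scores.
- *That any interval containing both 0 and .50 should be labelled inconclusive.* With the .25 criterion in place this would contradict it: d = .30, with interval -.22 to .81, would be both initial evidence and inconclusive.
- *That the bias is a main defect.* It is small and depends on a denominator the plan does not state.

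**Conclusion.** The point holds as a gap in the planned output, and it is worth correcting. With 15 pairs, a d of .25 to about .55 that the plan counts as initial evidence is compatible with no change, and a d between 0 and .25 is compatible with the plan's own medium effect. The planned output shows neither fact.

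The interval figures assume approximately normal change scores and d on the SD-of-change scale, which is inferred from the reproduction of .78. The 17% figure also assumes a true d of .50. The upward bias of about 6% is secondary.

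**What to change.** Change the effect-size sentence of the Analytic Plan to:

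> For each outcome we report the mean T1-T2 change with its 95% confidence interval, and the standardised change (SD of change, with Hedges' small-sample correction) with its 95% confidence interval; the small/medium/large labels are descriptive only.

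Apply the .25 reading to the corrected value, show it with its interval, and state where that interval includes 0. The plan is written in the past tense, so the change would be made in the report of these data.

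The cost is one sentence and extra table columns from data already collected. The downside is that d becomes about 5% smaller (an uncorrected .25 becomes .236, so an uncorrected d of about .264 is needed to reach .25), and the wide intervals are visible.

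Intervals do not reduce the uncertainty of a 15-family study; they let the reader see which effect sizes the data exclude.

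### Change and satisfaction are assessed only in families with T2 data, and this feasibility trial's plan gives no enrolled number and no retention analysis

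*Combined protocol and SAP*

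**What the plan says.** - **Purpose** (Participant Recruitment and Enrollment Procedures): "A feasibility trial was conducted to evaluate the FamilyNet program's feasibility, utilization, and user satisfaction in families of at-risk youth". Recruitment, screening and consent are described without counts.
- **Sequence** (Intervention and Assessment Procedures): consent and assent, T1, set-up call, three days of monitoring, Zoom session to build the plan, four weeks of use, T2. On timing: "At 4 weeks after T1, caregivers were administered the posttest (T2) caregiver questionnaire". No number is given at any step.
- **Satisfaction** (Measures): "The T2 caregiver and youth questionnaires also contained measures of caregivers' and youths' ratings of (5) satisfaction and acceptability". The Analytic Plan adds: "Examination of descriptive statistics for the user satisfaction and acceptability items at T2 informed on participants' reactions to the program".
- **Change** (Analytic Plan): "Paired t-tests were used to examine pretest-to-posttest change". The only sample size in the document is a count of complete pairs: "With 15 families with both T1 and T2 data, the study was powered to detect significant change in outcomes". The detectable effect is given as d > .78.
- **Threshold** (Analytic Plan): "we interpreted effect sizes of Cohen's d of .25 or greater as initial evidence".
- **Usage** (Measures; Analytic Plan): collected and summarised descriptively, with no stated denominator.

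The Analytic Plan's three goals are initial efficacy, participants' perceptions of the program, and usage. Retention is not among them.

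**The concern.** A paired t-test uses only families with both scores. A family with T1 but no T2 contributes nothing to the change result or to the satisfaction summary. The procedures contain several points at which a family could leave, and the plan neither counts families at those points nor says how a missing T2 is handled.

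Two things are at stake. First, if loss occurred and was related to severity or to change, the completers' mean change is biased, and the d = .25 threshold is low enough for this to matter. Second, retention is a basic feasibility result. The text is in the past tense and knows the number of completers, so the starting number could have been given.

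**Working it through.** **1. The plan's own figure.** Inputs: n = 15 pairs (Analytic Plan); two-sided alpha .05 and 80% power (assumed, not stated); d taken as mean change / SD of change (variant not stated). With df = 14 and noncentrality d√15, the noncentral t distribution gives a detectable d of .778, and power of 80.2% at d = .78. The stated figure reproduces. It is a statement about complete pairs.

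**2. Retention.** The enrolled N is not given, so these are assumed values with exact (Clopper-Pearson) 95% intervals:

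| Families at start | Retention with 15 completers | 95% CI |
|---|---|---|
| 15 | 100% | 78-100 (lower limit .025^(1/15) = .78) |
| 18 | 83% | 59-96 |
| 20 | 75% | 51-91 |
| 25 | 60% | 39-79 |

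**3. Possible bias in completers' change.** Simulation of 400,000 families with unit SDs, true change zero and T1-T2 correlation r = .5 or .7. Loss is logistic with log-odds 1 per score SD. Entries are spurious improvement in score SDs:

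| Loss depends on | r | 15% lost | 25% lost | 40% lost |
|---|---|---|---|---|
| T1 (milder families leave) | .5 | .069 | .106 | .168 |
| T1 (milder families leave) | .7 | .040 | .066 | .098 |
| Change (non-improvers leave) | .5 | .133 | .212 | .332 |
| Change (non-improvers leave) | .7 | .084 | .137 | .211 |

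If severer families leave instead, the sign in the first two rows reverses.

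**4. Against the d = .25 threshold.** The SD of change is √(2(1 − r)), which is 1.00 at r = .5 and .775 at r = .7. For change-dependent loss:
- 40% lost: .332/1.00 = .33 and .211/.775 = .27, both above .25. With the completers' own, slightly smaller SD of change they are .36 and .29.
- 25% lost: .212/1.00 = .21 and .137/.775 = .18, both below .25.

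**5. What a likelihood model on all T1 data recovers.**
- T1-dependent loss: the estimate is within .002 of zero.
- Change-dependent loss, from a repeat run: at r = .5, bias falls from .130/.210/.330 to .099/.162/.257, a reduction of 22-24% (for example 1 − .099/.130 = 24%). At r = .7 it falls from .083/.135/.211 to .071/.116/.182, about 14%.
- Overall error: with 15 completers of 18-25 families, its root mean squared error was no worse than the completer analysis (for example .264 against .293 at N = 20, r = .5).

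**6. Zero change in non-completers.** Take a completer d of .25 with unit SD of change. Then m = .25 × 15/N, variance = [14 + 15(.25 − m)² + (N − 15)m²]/(N − 1), and d = m/√variance. For N = 20: m = .1875, variance = (14 + .059 + .176)/19 = .749, d = .217. Likewise d = .235 at N = 17, .194 at N = 25 and .177 at N = 30.

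**The case against.** The strongest reply is that loss is nowhere documented. If 15 families enrolled, the paired t-test covers everyone and a mixed model returns the same result. This stands, so every statement about bias must be conditional.

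A reader might go further and infer that families who disliked the app skipped T2, so that the results are favourably biased. The documents do not support this. T2 was given online at a fixed time, with payment to caregiver and youth, and nothing ties it to app use. The bias could also run the other way.

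A reader might also infer that usage is summarised only in completers. The plan does not say so; its denominator is simply unstated. Nor is retention necessarily lost, since a results report could still give it. Asking about satisfaction only after use is inherent to such ratings; what it needs is a response rate.

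The model can be criticised too. It does little if loss depends on change. It treats families with T1 only, including any never set up, as if they followed the completers' T1-T2 relation, whereas the plan asks about change after engaging with the program. With 15 completers of 18-25 families, the estimate's standard deviation is about .20-.26 under either method, larger than the T1-dependent bias of .04-.17. These points stand. They are reasons to place the model beside the paired t-test and to add a sensitivity analysis. They do not remove the need for the counts, which alone show whether bias is possible.

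**Conclusion.** The point holds as an omission with a conditional consequence. The plan analyses change in complete pairs and satisfaction in T2 responders, and gives no enrolled number, retention analysis or missing-data method in a trial whose stated purpose is feasibility. Whether any bias exists, and which way it runs, cannot be known from the documents. The sizes above rest on assumed loss of 15-40%, r of .5-.7, no true change and a logistic loss mechanism. Within that range, only the 40% non-improver case takes a null effect past d = .25. The d > .78 power figure is not in dispute. The change should be made, but nothing here shows the results to be wrong.

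**What to change.** 1. Make retention a feasibility result. Report numbers consented, T1 completed, app set up, plan built and T2 completed (caregiver and youth separately), each proportion with an exact 95% CI.
2. Beside the paired t-test, estimate change from all families with T1 by a REML mixed model (time effect, unstructured 2×2 covariance, Kenward-Roger df). State that it equals the paired t-test if no T2 is missing, corrects loss that depends on T1, and removes only about 14-24% of the bias if loss depends on change. For that reason, add a sensitivity analysis assigning zero change to non-completers.
3. Summarise usage over all consented families, counting those never set up as non-users, and state that denominator.
4. Show satisfaction beside the T2 response rate. Compare T1 scores by T2 status, and usage where logs exist; a family lost before the set-up call has T1 scores but no log.

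The cost is a small extra analysis of data that should already be held. The downside is that retention, usage and change figures may look less favourable. If retention was complete, the change estimate is unaltered.
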